5.6. Medical Devices

- 1. The devices manufactured for Pfizer by a third party provided for use in this study are:
 - a. pre-filled syringes for subcutaneous injection of dupilumab (manufactured by Sanofi-Regeneron followed by relabeling and repackaging for Pfizer by a third party);
 - b. pre-filled syringes for subcutaneous injection of matching placebo.
- 2. Instructions for medical device use are provided in the Dosing Instructions.

3. Pre-filled syringe medical device incidents, including those resulting from malfunctions of the device, must be detected, documented, and reported by the investigator throughout the study (see Section 8.4.5).

5.7. Investigational Product Storage

The investigator, or an approved representative, eg, pharmacist, will ensure that all investigational products are stored in a secured area with controlled access under required storage conditions and in accordance with applicable regulatory requirements.

Investigational product should be stored in their original container and in accordance with the labels. See the Investigational Product Manual (IP Manual) for storage conditions of the product.

Any storage conditions stated in the SRSD will be superseded by the storage conditions stated on the product label.

Site systems must be capable of measuring and documenting (for example, via a log), at a minimum, daily minimum and maximum temperatures for all site storage locations (as applicable, including frozen, refrigerated, and/or room-temperature products). This should be captured from the time of investigational product receipt throughout the study. Even for continuous-monitoring systems, a log or site procedure that ensures active evaluation for excursions should be available. The intent is to ensure that the minimum and maximum temperature is checked each business day to confirm that no excursion occurred since the last evaluation and to provide the site with the capability to store or view the minimum/maximum temperature for all non-working days upon return to normal operations. The operation of the temperature monitoring device and storage unit (for example, refrigerator), as applicable, should be regularly inspected to ensure they are maintained in working order.

Any excursions from the product label storage conditions should be reported to Pfizer upon discovery. The site should actively pursue options for returning the product to the storage conditions described in the labeling, as soon as possible. Deviations from the storage requirements, including any actions taken, must be documented and reported to Pfizer.

Once an excursion is identified, the investigational product must be quarantined and not used until Pfizer provides documentation of permission to use the investigational product. It will not be considered a protocol deviation if Pfizer approves the use of the investigational product after the temperature excursion. Use of the investigational product prior to Pfizer approval will be considered a protocol deviation. Specific details regarding information the site should report for each excursion will be provided to the site in the IP Manual.

Receipt of materials, door opening and closing, and other routine handling operations where the products are briefly out of the temperature range described in the labeling are not considered excursions.

Site staff will instruct subjects on the proper storage requirements for take home investigational products.

5.8. Investigational Product Accountability

The investigator site must maintain adequate records documenting the receipt, use, loss, or other disposition of the investigational product supplies. All investigational products will be accounted for using a drug accountability form/record. To ensure adequate records, all drug supplies will be accounted for in the drug accountability inventory forms as instructed by Pfizer and will be monitored by the accounting of unused investigational product returned by the subjects. At the end of the clinical trial, all drug supplies unallocated or unused by the subjects must be returned to Pfizer or its appointed agent, or destroyed in an approved manner unless otherwise authorized by Pfizer. In either case, the forms must identify the investigational product, including batch or code numbers, and account for its disposition on a subject-by-subject basis, including specific dates and quantities.

All bottles of oral investigational product must be brought back to the site at every visit for inspection by the site staff and all bottles/unused oral investigational product must be returned to the investigator by the subject at the relevant visit(s).

Subjects will be directed to bring any used and unused syringe cartons to all visits for inspection by the site staff. Study sites will provide subjects with a sharps container for disposal of used syringes. Subjects will return this sharps container to the study site at the final visit for disposal.

5.8.1. Destruction of Investigational Product Supplies

The sponsor or designee will provide guidance on the destruction of unused investigational product (eg, at the site). If destruction is authorized to take place at the investigator site, the investigator must ensure that the materials are destroyed in compliance with applicable environmental regulations, institutional policy, and any special instructions provided by Pfizer, and all destruction must be adequately documented.

5.9. Concomitant Treatment(s)

Subjects will abstain from all concomitant medications as described in Section 4.2 and Appendix 3 of the protocol. Medications that are taken in the Screening/Washout period (after informed consent is obtained and before the first dose of investigational product) will be documented as prior medications. Medications taken after the first dose of investigational product has been administered will be documented as concomitant medications. All concomitant medications taken during the study must be recorded in study records with indication (if atopic dermatitis), reference to any associated adverse event, dose, and start and stop dates of administration. Subjects will be queried about concomitant medication (including topical medications and treatments, over-the-counter and prescription medications and treatments, and vaccinations) at each study visit. Any new concomitant medications or dose changes to current concomitant medications should be evaluated for potential new or worsening adverse events.

5.9.1. Permitted Concomitant Medications

Background Topical Therapy

Subjects must comply with standardized background topical therapy guidance throughout the study. Background topical therapy will not be provided by the sponsor. Standardized background topical therapy refers to the below, in accordance with the local standard of care and according to the Investigator's usual practice:

Non-medicated Topical Therapy

• Non-medicated topical emollient without other active ingredients indicated to treat AD, or other additives which could affect AD (eg, hyaluronic acid, urea, ceramide or filaggrin degradation products): must be applied at least twice daily to all body areas affected with AD, throughout at least the final 7 days prior to Day 1 and throughout the remainder of the study.

Medicated Topical Therapy

- Topical Corticosteroids (TCS) must be applied once daily to areas with active lesions, starting on Day 1 (Baseline) and throughout the study, according to the guidance below:
 - Medium potency TCS (eg, Triamcinolone acetonide 0.1% cream or fluocinolone acetonide 0.025% ointment) must be applied to body areas with active lesions that are suitable for the use of medium potency TCS. Subjects must be clinically monitored for toxicity to topical steroids and stepped down as needed.
 - After lesions are under control (clear or almost clear), treat once daily for a further 7 days, then stop;
 - If lesions return then resume treatment with medium potency TCS, but use the approach described above upon lesion resolution.
 - Low potency TCS (ie, hydrocortisone 1% cream) must be applied to body areas of thin skin (face, neck, intertriginous, and genital areas, areas of skin atrophy, etc.) with active lesions instead of medium potency TCS or to body areas where continued treatment with medium potency TCS is considered unsafe. Subjects must be clinically monitored for toxicity to topical steroids and stepped down as needed.
 - After lesions are under control (clear or almost clear), treat once daily for a further 7 days, then stop;
 - If lesions return then resume treatment with low potency TCS, but use the approach described above upon lesion resolution.

• Topical calcineurin inhibitors (eg, tacrolimus, pimecrolimus) or a PDE4 inhibitor (eg, crisaborole) may be used instead of corticosteroids in body areas of thin skin (face, neck, intertriginous, and genital areas, areas of skin atrophy, etc.) with active lesions or if continued treatment with TCS of any potency is considered unsafe, and according to locally approved label at the investigator's discretion and considering prior response or intolerance to these medications.

NOTE: Background topical therapy must not be applied prior to attending a study visit, on the day of the study visit. Background topical therapy instead should be applied after the visit, on study visit days.

Other Concomitant AD Therapies

The following other concomitant AD therapies are permitted during the study and will not be provided by the sponsor:

• Oral antihistamines.

The following concomitant medications are permitted during the study:

- Corticosteroid inhalers and intranasal sprays are permissible for subjects receiving a stable dose;
- Ophthalmic corticosteroids are permissible for subjects receiving a stable dose;
- Low dose acetyl salicylic acid (≤100 mg QD) is permitted, for the purpose of cardiovascular prophylaxis, at the discretion of the investigator;
- Acetaminophen/paracetamol may be used intermittently;
- Vitamin and mineral supplements of standard potency are allowed in amounts not known to be associated with adverse effects (such as hyper-vitaminosis).

For the purposes of this protocol, dietary supplements are defined as vitamins, minerals, and purified food substances. Vitamins, minerals and purified food substances are allowed in amounts not known to be associated with adverse effects (such as hyper-vitaminosis).

Unless a prohibited medication or treatment, subjects may be administered any other medications necessary for the treatment of concomitant medical disorders as deemed necessary by the treating physician. Following Day 1, addition of concomitant medications or any change in the dosage should be limited to those considered medically essential.

A subject who is receiving a permitted concomitant medication for any reason must be on a locally-approved medication and dose, and this must be documented in the CRF. Subjects are not allowed any other investigational drugs or treatments during the study.

Subjects should refrain from starting new or changing doses of permitted prescription or non-prescription drugs, vitamins, and dietary supplements within 7 days or 5 half-lives (whichever is longer) prior to Day 1 and prior to study visits throughout the study, unless otherwise noted below.

Subjects should report any changes to permitted medications during the study to the investigator as soon as they occur. Medication changes must be documented in the subject's record and CRF.

5.9.2. Prohibited Medications and Treatments

Subjects are required to discontinue and avoid using certain medications and treatments (see Inclusion Criteria and Exclusion Criteria, and Appendix 3). Subjects should be instructed at each visit to contact the study site investigator promptly if there are any intended changes or additions to concomitant medications.

All medications and treatments that could affect atopic dermatitis must be discontinued except oral antihistamines. Medicated topical therapy for AD must be washed out one week prior to Day 1 (Baseline). Starting on Day 1, standardized background topical therapy will be used as per protocol guidance in Section 5.9.1.

Due to the potential to affect atopic dermatitis with ultraviolet light exposure, subjects must also avoid prolonged exposure to the sun and not to use tanning booths, sun lamps or other ultraviolet light sources during the study.

Subjects who received prior treatment with systemic JAK inhibitors are to be excluded from the study. Prior treatment with topical JAK inhibitors is not exclusionary.

Herbal medications with unknown properties or known beneficial effects for AD must be discontinued at least 4 weeks before the first dose of investigational product.

Restrictions on certain vaccinations are described in Section 4.2.

The Pfizer study team is to be notified of any prohibited medications taken during the study. After consulting with the Medical Monitor, the investigator will make a judgement on the ongoing eligibility of any subject with prohibited medication use during the study.

6. STUDY PROCEDURES

Refer to the Schedule of Activities for a detailed list of study procedures, as they should be conducted at each respective visit.

Due to possible need for PPD testing and chest radiograph, screening procedures may be performed over more than 1 visit in the 28 days prior to the Day 1 visit.

Visit windows are based on Day 1 visit. To assure consistency and reduce variability, all study visits should occur in the morning whenever possible. On days of study visits, subjects will receive their dose at the clinic during the visit.

Subjects are required to fast for at least 8 hours prior to all visits that include lipid profile panel testing (Day 1, Week 4, Week 16, Week 20 and EOS). During the fasting period, subjects should refrain from all food and liquids (water and permitted non-study medications are allowed).

ECGs will be interpreted by a central reader for all visits.

Urine pregnancy test must be performed prior to dosing with the investigational product for female subjects of childbearing potential through to the EOS visit.

Prior to attending a study visit, subjects are allowed to shower and bathe but should not moisturize or apply emollient.

Refer to Appendix 4 for guidelines on subject safety monitoring and discontinuation.

6.1. Visit 1, Screening

Subjects will be screened (Visit 1) within 28 days prior to administration of the investigational product to confirm that they meet the subject selection criteria for the study. The investigator (or an appropriate delegate at the investigator site) will obtain informed consent from each subject in accordance with the procedures described in Subject Information and Consent in Section 12.3.

If the Mantoux PPD tuberculin skin test is given, the subject must return between 48-72 hours post-injection for induration evaluation.

Screening laboratory tests with abnormal results may be repeated once to confirm abnormal results; the last value will be used to determine eligibility. If results return to normal within the 4-week screening period, the subject may enter the study.

The following procedures will be completed:

- Obtain written informed consent:
- Register subject using the IRT system;
- Collect demography;
- Administer C-SSRS and PHQ-8. Subjects meeting any of the criteria specified in Exclusion Criterion 2 as described in Section 4.2 on the C-SSRS or PHQ-8 should be excluded from participation; it is recommended the subject's primary care physician (PCP) should be informed, and the subject referred to a mental health professional, either by the PCP or the investigator according to their usual practice;
- Obtain weight;
- Obtain height;

- Obtain vital signs including pulse rate, sitting blood pressure, respiratory rate and oral or tympanic temperature (after at least 5 minutes of rest);
- Complete medical history, including history of alcohol and tobacco use. Smoking status and average weekly alcohol consumption (units/week) will also be collected, where a unit contains 12 g of pure alcohol, an amount equivalent to that contained in 5 oz/150 ml (a glass) of wine, 12 oz/360 ml of beer, or 1.5 oz/45 ml of 90 proof (45% alcohol by volume) of spirits;
- Obtain complete medication history of all prescription or nonprescription drugs, and dietary and herbal supplements taken within 28 days prior to the planned first dose, except as noted below:

The following timeframe prior to the planned first dose must be used for collection of the following Current/Prior Medications:

- 1 year: Previous drug treatments for AD including the use of topical treatments and other treatments (excluding systemic);
- Lifetime history of previous systemic treatment for AD and reason for stopping any systemic treatment for AD;
- Lifetime history of intolerance/allergy to any drug, regardless of indication;
- Complete AD disease history includes collection of details of AD: AD diagnosis and duration, the use of topical treatments, systemic treatments and other treatments for AD;
- Train subject on protocol guidance for the use of background topical therapy as described in Section 5.9.1;
- Conduct complete physical examination;
- Conduct clinical evaluations including IGA, SCORing Atopic Dermatitis (SCORAD), EASI and BSA (calculated in the EASI);
- Assess need for contraception and adherence to applicable lifestyle requirements (Section 4.4). Establish willingness and ability to comply with lifestyle requirements going forward in the study;
- Perform a single 12-lead electrocardiogram (ECG). Clinically significant or exclusionary ECG findings require screen failure;
- Review Inclusion and Exclusion criteria for subject eligibility;
- Assess for occurrence of Adverse Events: The adverse event and SAE reporting period starts with the signing of the informed consent document;

- Tuberculosis Test QuantiFERON® TB Gold In-Tube test or locally analyzed T-SPOT®. TB test (Japan only) (unless performed within 12 weeks of Day 1). If Mantoux PPD tuberculin skin test is required to be performed instead, per Section 7.3.4, the subject must return between 48-72 hours post-injection for evaluation of induration (see Section 7.3.4 for further details on TB testing);
- Chest X-ray (posterior-anterior and lateral views) or other appropriate diagnostic image (ie, computerized tomography [CT] or magnetic resonance imaging [MRI]) are required. Official reading must be located and available in the source documentation. Chest X-ray may be performed up to 12 weeks prior to Day 1;
- Obtain samples for laboratory testing: serum chemistry, hematology (including coagulation panel), coagulation panel), serum FSH (female subjects of childbearing potential) or serum pregnancy test (female subjects of childbearing potential), HIV, hepatitis B surface antigen (HBsAg), hepatitis B core antibody (HBcAb), hepatitis B surface antibody (HBsAb), hepatitis C viral antibody (HCV Ab), hepatitis C viral ribonucleic acid (HCV RNA) (see Section 7.6.2.1);
- For China, Republic of Korea, and Taiwan only: Collect sample for HBV DNA reflex test (see Section 7.6.2.1);
- For Japan only: In addition to HBsAg and HBcAb, HBsAb testing will be performed at Screening for all subjects rather than as a reflex test. Subjects with negative results for HBsAg, HBcAb and HBsAb may be eligible. Subjects who are HBsAg negative, HBcAb negative and HBsAb positive and provide documentation of prior HBV vaccination may be eligible and will not require HBV DNA monitoring during the study. Subjects who are HBsAg negative, HBcAb negative and HBsAb positive without documentation of prior HBV vaccination AND subjects who are HBsAg negative, HBcAb positive, and HBsAb positive at screening will have reflex testing for HBV DNA. Subjects who are HBV DNA negative or below LLQ may be randomized but will have HBV DNA repeated at Week 12 and Week 20 End of Treatment (EOT) visit, or Early Termination (ET) visit, whichever is sooner;
- Dispense eDiary and instruct subject in how to use the device. Instruct the subject to begin daily completion of the Pruritus and Symptoms Assessment for Atopic Dermatitis (PSAAD) (in selected countries), Pruritus NRS,
 - Pruritus NRS CCI will be collected daily in a subject eDiary during the screening period and from Day 1 to 15 and then on study visit days;
 - PSAAD will be collected daily in a subject eDiary during the screening period and from Day 1 through the End of Study visit, in selected countries;

• Instruct the subject to keep a daily record of use of standardized background topical therapy. Standardized background topical therapy use and adherence with guidelines will be recorded daily in the subject eDiary during the screening period and through the End of Study visit;

• If the subject is eligible for continued participation, provide subject with emergency contact card.

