3.4. Baseline Variables

In general, for all analyses, baseline will be defined based on observations collected prior to first dose. For DLQI, EQ-5D-5L, FACIT-F, HADS, POEM, PtGA, baseline will be defined based on observations collected on or prior to the day of first dose. Baseline values for demographics, medical and other history, atopic dermatitis history will be based on measures collected at Visit 1 / Screening visit. Study Day 1 is defined as the day the subject receives first dose of study drug. For purposes of all other analyses including analyses for change from baseline, the baseline value will be defined as measured on Day 1 (before time of first dose, if time is available). If a value is missing on Day 1, then the last available observation before Day 1 will be used. For the PSAAD score, baseline will be defined as the average of all values recorded from Day -6 until Visit 2 / Day 1.

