5.2.3. Analyses of Longitudinal Continuous Data

Mixed-effect, repeated measures (MMRM) models will be used. The fixed effects of treatment, visit, treatment-by-visit interaction and baseline disease severity will be included. Visit will be modeled as a categorical covariate. Unstructured covariance matrix will be assumed for the model errors. Compound symmetry covariance matrix will be used if the model with unstructured covariance doesn't converge.

When modeling the change from baseline values, the variable for visit will start with the first post-baseline visit, and the actual baseline value will be included as a covariate. At each visit, estimates of least square mean (LSM) values and the LSM differences between treatment groups will be derived from the model. The corresponding p-values and 95% confidence intervals will also be derived from the model. In the model all patients with baseline data are used for estimating baseline covariate effects and adjusting LS means.

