6.5. PRO Endpoints

6.5.1. Continuous Endpoints

- Endpoints:
 - Weekly Change from Baseline (up to Week 16) in Total PSAAD Score;
 - Weeks 2, 4, 8, 12, and 16 Change from Baseline in PtGA;
 - Weeks 2, 12 and 16 Change from Baseline in DLQI;
 - Weeks 12 and 16 Change from Baseline in HADS (separate for anxiety and depression), POEM, EQ-5D-5L;
- Summary: Change from Baseline for each specified time points;
- Population: FAS;
- Statistical Method: MMRM in [Section 5.2.3](#). As PSAAD is collected daily, data will be summarized weekly using a simple average of the values recorded within a week;
- Missing Data: Observed Data.

090177e1937d0b4e\Approved\Approved On: 18-May-2020 15:17 (GMT)

CCI

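### The MMRM of percent change in pruritus NRS adjusts for one day's itch score and leaves the other pre-dose diary scores unused, so its confidence intervals are somewhat wider than they need be

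*Protocol*

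**What the plan says.** - **Collection.** Protocol 6.1 states that Pruritus NRS "will be collected daily in a subject eDiary during the screening period and from Day 1 to 15 and then on study visit days". Protocol 7.10.1 describes NRS severity as one item on the worst itch over the past 24 hours.
- **Baseline.** SAP 3.4 names several patient-reported outcomes with their own rule. NRS is not among them, so it takes the default, under which "the baseline value will be defined as measured on Day 1 (before time of first dose, if time is available". There is a fallback: "If a value is missing on Day 1, then the last available observation before Day 1 will be used". Either way the baseline is one score.
- **Model.** SAP 5.2.3 says that for change from baseline "the actual baseline value will be included as a covariate". SAP 6.4.3 applies this MMRM to percent change in NRS severity on each of Days 2 to 15 and at Weeks 4, 8, 12 and 16.
- **PSAAD.** For this second diary instrument, SAP 3.4 says "baseline will be defined as the average of all values recorded from Day -6 until Visit 2 / Day 1", and SAP 6.5.1 says its "data will be summarized weekly using a simple average of the values recorded within a week".
- **The week before dosing.** Inclusion criterion 4 allows only emollient as AD treatment during the last 7 days before Day 1.

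**The concern.** A single 24-hour itch rating measures a subject's usual itch with error. When such a score is the only baseline covariate, it removes less between-subject variation than a mean of several days would. The extra scores are collected before randomisation and are already in the database.

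What is at stake is interval width. Under SAP section 6, this endpoint gets p-values against placebo only. The contrast with dupilumab is reported as an estimate with a 95% confidence interval, so the width of that interval largely determines how informative the comparison is. Direct comparison with dupilumab on itch is a stated aim of the study (Protocol section 3).

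**Working it through.** **1. The plan's own itch figure.** Protocol 9.1 claims at least 92% power for Week 2 NRS4, 18% against 33%, with 200 per arm at two-sided 5%.
- Pooled SE = √(2 × 0.255 × 0.745 / 200) = 0.0436.
- Unpooled SE = √((0.18 × 0.82 + 0.33 × 0.67) / 200) = 0.0429.
- z = (0.15 − 1.96 × 0.0436) / 0.0429 = 1.50, so power is 93.4%.

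The figure is reproduced. It uses response rates only, so it does not depend on how a continuous baseline covariate is defined.

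**2. Which NRS analyses use the baseline score as a covariate.**

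| Analysis | Method | NRS covariate? |
|---|---|---|
| NRS4 at Week 2 (key secondary) | CMH by disease severity (SAP 5.2.1, 6.3.1) | No |
| NRS4 step-down, Day 15 to Day 2 | CMH (SAP 5.1, 6.4.1) | No |
| Time to NRS4 | Stratified log-rank (SAP 5.2.5, 6.4.2) | No |
| Percent change in NRS | MMRM (SAP 5.2.3, 6.4.3) | Yes, one score |

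Only the last row can gain.

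**3. Analytic check on the size.** Let r be the correlation between two pre-dose days and ρ the correlation of a single-day baseline with the post-baseline score. Both are assumed; the documents give neither. With equal correlation between days, the residual variance using a 7-day mean, relative to one day, is

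[1 − ρ²/s²] / (1 − ρ²), with s² = (1 + 6r)/7.

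For r = 0.7, s² = 5.2/7 = 0.743.
- ρ = 0.3: 0.8788 / 0.91 = 0.966, a variance cut of 3.4% (SD 1.7%).
- ρ = 0.4: 0.7846 / 0.84 = 0.934, a cut of 6.6% (SD 3.4%).
- ρ = 0.5: 0.6635 / 0.75 = 0.885, a cut of 11.5% (SD 5.9%).

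**4. Simulation of the proposed change.** The outcome is Week 2 percent change with the Day 1 score as denominator, on integer 0 to 10 scores with Day 1 ≥ 4. The model with the Day 1 covariate is compared with the model using Day 1 plus the 7-day mean. Assumptions: mean 6.5, single-day reliability 0.5 to 0.8, SD of true change 1.5 to 2.5 points. A fall f in residual SD is worth 1/(1 − f)² − 1 in sample size.

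| Setting | Fall in residual SD | Equivalent extra subjects |
|---|---|---|
| Seven entries, no drift, daily noise independent or with autocorrelation 0.5 | 2.5% to 7.6% | 5% to 17% |
| Autocorrelation 0.5, with either subject-varying drift (slope SD 0.25 points/day) or only three entries | 1.2% to 3.3% | 2.5% to 7% |

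End points: 1/0.924² = 1.17 and 1/0.988² = 1.024. One case for illustration, at the favourable end (reliability 0.61, SD of change 1.5): residual SD falls from 34.0 to 31.5 with independent noise (7.4%), or from 34.0 to 32.3 with autocorrelation 0.5 (5.0%). The treatment estimate moved by at most 0.13 percentage points, so the gain is in precision only.

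**5. Why the mean should not replace the Day 1 baseline for NRS4.** Starting from 93.4% power, scoring NRS4 against a raw 7-day mean gives 91% to 94% with no drift, and 84% to 89% if itch rises by 0.15 points/day in the last week. A mean rounded to an integer gives 94% to 97.5% and 90.5% to 94% respectively. There is no consistent gain, and the endpoint itself would change.

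**The case against.** The strongest reply is that the plan's choice is valid, pre-specified and unbiased, and that only one analysis without multiplicity control is touched (SAP 5.1). That is right, and it sets the severity. Further points:

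- **PSAAD.** A reader might infer that the SAP is inconsistent in averaging PSAAD but not NRS. It is not. PSAAD outcomes are weekly means, so its averaged baseline matches them. NRS outcomes on Days 2 to 15 are single-day scores (SAP Appendix 2), and after Day 15 NRS is collected only at visits, so a one-day NRS baseline is like for like. This bears on how change is defined; a covariate need not be measured in the same way as the outcome.
- **Run-in.** A reader might treat Day -6 to Day 1 as a stable run-in. The documents fix the regimen, not the itch: medicated topicals need stop only one week before dosing, so this can be the first week after withdrawal. A uniform rise of 0.15 points/day left the gain unchanged (7.5% against 7.6% in one case), but drift that differs between subjects reduces it, as shown above.
- **Diary completeness.** Screening has no stated minimum length, and subjects who cannot use the handheld device may still take part (Protocol 7.10). With three entries the gain is at the low end.
- **Reach of the simulation.** Only Week 2 was simulated; the gain at Weeks 4 to 16 is not established.

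These points shrink the gain but do not remove it.

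**Conclusion.** The point holds as a modest loss of precision in one secondary analysis, the MMRM of percent change in NRS severity. Over the assumptions tried, the unused scores are worth about 1% to 8% of residual SD, and confidence intervals would narrow by about the same proportion. No NRS variance or day-to-day correlation is given in the documents, so the range cannot be tightened.

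Two stronger readings are not supported. A reader might infer that every NRS analysis loses precision, including the Week 2 key secondary comparison with dupilumab; those analyses carry no NRS covariate. A reader might also infer that the evidence on itch onset is weakened; SAP 5.1 assigns onset to the NRS4 step-down, which is unaffected. There is no bias and no effect on type I error. Severity: optional, minor.

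**What to change.** In SAP 5.2.3 or 6.4.3, before unblinding, add to the NRS percent-change MMRM a second baseline covariate: the mean of the available daily NRS severity scores from Day -6 to pre-dose Day 1, or the Day 1 value if there is no other entry. Keep the Day 1 score as the existing covariate, for eligibility, for the NRS4 definition and as the percent-change denominator, so that no endpoint changes. If the sponsor prefers the single-day covariate, one sentence giving the reason would do, with the two-covariate model as a sensitivity analysis.

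Cost: one sentence of SAP text, one derived variable, one extra model term and a rule for sparse diaries. No new data are needed.
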